### 3 Introduction

#### 3.1 Preface

Chronic low back pain (cLBP) affects an estimated 42 million Americans and is associated with greater healthcare utilization, higher rates of unemployment, worse sleep and more depression compared to those without cLBP. The most widely used treatment options for cLBP typically include a combination of medication and surgical procedures, with the goal of relieving pain and restoring

function. Unfortunately, despite advances in pain management, medical interventions alone frequently cannot resolve cLBP, leaving many patients with a significant amount of pain and limited functioning. It is now widely accepted that optimal management for cLBP includes treatments that address not just the biological cause, but also the role of psychosocial factors in the development and maintenance of chronic pain.

At present there are data suggesting a variety of structural/mechanical, neural, psychological, cognitive, behavioral, social, and economic contributors to cLBP. Acknowledgement of this complex set of pathogenic factors in the etiology and maintenance of cLBP is referred to as the biopsychosocial model of chronic pain. The BACPAC initiative has chosen to address the many facets of the biopsychosocial model in a comprehensive and unbiased manner and provide an integrated translational approach to identifying both the underlying mechanisms operative in cLBP, as well as the treatments that work on those underlying mechanisms.

### 3.2 Study Scope and Objective

The objective of this study is to establish a cohort of cLBP patients in order to conduct a pragmatic clinical trial of four cLBP treatments. Rich phenotypic data will be collected for each patient which will allow investigators to assess which evidence-based cLBP treatments are most effective for different cLBP patient subpopulations.

## 4 Study Aims and Endpoints

### 4.1 Study Aims

**Aim 1: To perform an Interventional Response Phenotyping study in a cohort of cLBP patients. We will perform a pragmatic trial using a cohort of cLBP patients, who will receive a sequence of interventions known to be effective in cLBP.** For 4 weeks, all cLBP participants will receive a web-based behavioral self-management program for pain. After the four weeks, individuals with significant levels of pain interference will be enrolled in a Sequential, Multiple Assessment, Randomized Trial (SMART) and randomized to a series of treatments, including: a) mindfulness-based stress reduction (n=102), b) physical therapy and exercise (n=102), c) acupressure self-management (n=102), or d) duloxetine (n=102). After 8 weeks, individuals who remain symptomatic will be re-randomized to a different treatment for an additional 8 weeks.

**Aim 2: To demonstrate that currently available, clinically derived measures, can predict differential responsiveness to common cLBP therapies.** We will leverage the SMART design to perform the most comprehensive study-to-date of currently available predictors for commonly used cLBP therapies. All patients enrolled in Aim 1 will complete baseline clinical phenotyping that will include the following potential predictors of treatment response: a) demographics, b) questionnaires assessing underlying pain mechanisms, c) ambulatory symptom monitoring, d) extensive psychological assessment using validated patient-reported outcomes, e) structured physical examination, and f) state-of-the-art structural imaging of the back and pelvis.

**Aim 3: To identify new experimental measures that predict differential responsiveness to each of the above therapies, as well as to infer mechanisms of action of treatments.** A subset of individuals (n=160) from the larger cohort in Aims 1 and 2 will be asked to participate in an expanded phenotyping study that will include functional neuroimaging, quantitative sensory testing, plasma measures of inflammation, and autonomic tone.

## 4.2 Statistical Analysis Objectives

The above study objectives have been translated into the following statistical analysis objectives:

**Objective 1:** Assess differential treatment response using the light and deep phenotype data.

**Objective 2:** Given a patient phenotype, identify the best initial treatment for the patient.

[figure not shown]
**Objective 3:** Identify the mechanisms that explain the causal treatment effects.

## 4.3 Endpoints

The primary study endpoint is the change in the PROMIS (Patient-Reported Outcomes Measurement Information System) pain interference score between the T2 pre-intervention visit and T3 post-intervention visit. The PROMIS pain interference measures the degree to which a patient's pain interferes with the patient's life. The survey questions assess interference in different domains including work around the home, recreational activities, and social activities. A univariate pain interference score is calculated from the respondent's answers. This process is described in Section 9.2.

The study's secondary endpoints consist of the change in the Pain Intensity (PEG) and the Patient Global Impression of Change (PGIC) between the T2 pre-intervention visit and T3 post-intervention visit. The other exploratory PROMIS measures will include a measure of physical functioning, fatigue, sleep disturbances, and cognition. The process of computing each secondary endpoint from survey responses is found in Section 9.2.

Figure 1 Study aims and overview

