1.1 Synopsis

Title:	University of Michigan Mechanistic Research Center (BACPAC Study)
Grant Number:	1U19AR076734-01
Study Description:	A long-term pragmatic trial in a cohort of patients with chronic low back pain (cLBP). Using a sequential, multiple assignment, randomized trial (SMART) study design. This will consist of a 4-week run-in period using an online cognitive-behavioral self-management intervention (PainGuide), followed by two 8-week treatment periods. Participants between the ages of 25–70 years old who have cLBP and who are eligible will be followed for approximately nine months. Those who have had minimal or modest improvement in their pain (PGIC≥2) after the PainGuide run-in period will be randomized to one of the four 8-week long interventions. These interventions are Mindfulness-Based Stress Reduction (MBSR), physical therapy (PT) and exercise, acupressure self-management, or duloxetine. After that first 8-week treatment, participants with minimal or modest improvement in their pain (PGIC≥2) will be randomized to a second treatment (one of the three treatments not received before). A subset of participants will complete an additional deep phenotyping assessment.
Objectives*:	
Primary Objective: To perform an Interventional Response Phenotyping study in a cohort of cLBP patients.
 
Secondary Objectives:
 
1. To demonstrate that currently available, clinically-derived measures, can predict differential responsiveness to the above therapies2. To identify new experimental measures that predict differential responsiveness to each of the above therapies, as well as to infer mechanisms of action of these treatments.
Endpoints*:	
1. Primary Endpoint: Pain Change in PROMIS Pain Interference between T2 and T3 study visits2. Secondary Endpoints:
a. Change in the Pain, Enjoyment and General Activity (PEG) Scale between T2 and T3 study visits.b. Change in Patient Global Impression of Change (PGIC) between T2 and T3 study visits
Study Population:	Participants between the ages of 25–70 years old who have cLBP
Description of Sites/Facilities Enrolling Participants:	This study will recruit from 6 outpatient clinics catering to low back pain patients at the Michigan Medicine. There will be no sites outside of the US.

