9.4.5 Medication Accountability

All study medication bottles will be collected/returned from the participant to the study team. When a bottle is returned, a study team member will count how many capsules or left and record the number on the bottle, date and initials. All medication bottles will be returned to the Research Pharmacy for drug accountability. The Research Pharmacy will be asked to sign off on the accountability log showing the bottle is returned. The Research Pharmacy will dispose of medication and bottles.

10 Deep Phenotyping Visits

A subset of study participants (n=160) be offered optional deep phenotyping. These participants will have a separate assessment appointment with study personnel at the CPFRC. There will be two visits that take place after T2-before Treatment 1 and after T3-before Treatment 2. At the deep phenotyping study visit, participants will undergo QST, Structural and functional brain neuroimaging, inflammatory markers assessment and the assessment autonomic functioning.

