## Statistical Analysis Plan

Force Minimum Dataset*																				
Low Back Pain-Specific Pain Intensity*		X		X	X			X	X			X			X	X	X	X	X	X
Opioid use- Single-Item Current Opioid Use*		X		X	X			X	X			X			X		X			
Pain Intensity (PEG)*		X			X				X			X			X		X			
PROMIS Physical Functioning 6b*		X		X	X			X	X			X			X	X	X	X		
PROMIS Anxiety 4a*		X		X	X			X	X			X			X	X	X	X		
PROMIS Depression-4		X		X	X			X	X			X			X	X	X	X		
PROMIS Fatigue		X		X	X			X	X			X			X	X	X	X		
PROMIS Sleep Disturbance 6a*		X		X	X			X	X			X			X	X	X	X		
Sleep Duration*		X		X	X			X	X			X			X	X	X	X		
PROMIS Social Role Activity		X		X				X				X			X	X	X	X		
PROMIS Pain Interference 4a*	X	X		X	X			X	X			X			X	X	X	X	X	X
PROMIS Cognitive Function		X		X	X			X	X			X			X	X	X	X		
PROMIS Pain intensity		X		X	X			X	X			X			X	X	X	X	X	X
Pain Catastrophizing Scale (PCS)*		X		X	X			X	X			X			X		X			
Patient Health Questionnaire-2 (PHQ-2)*		X			X				X								X			

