## 9 Analysis Plan

### 9.1 Objective 1 Analysis Plan

**Objective 1:** Assess differential treatment response using the light and deep phenotype data. The main hypotheses of Objective 1 will be addressed by fitting a joint regression model the primary pain outcome (PROMIS pain interference score) at time point T3 which gains efficiency by incorporating observations at time point T4. The purpose of this analysis is to demonstrate that clinical measures are capable of predicting differential responsiveness to the four cLBP treatments. This analysis will assess the degree to which the clinicians' hypothesized treatment modifiers predict differential treatment response. Testing the differential treatment response hypotheses will be handled by including treatment-phenotype interactions in the model. The analysis will be repeated for the secondary pain outcomes (Pain intensity (PEG) and Patient Global Impression of Change (PGIC)).

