#### 9.1.1 Light Phenotyping Analysis

Let  $Y_{ti} \in \mathbb{R}$  denote subject  $i$ 's PROMIS pain interference score at time  $t \in \{2, 3, 4\}$ . Let  $R_i$  denote response status at T3. Let  $A_{ti}$  be a vector denoting treatment assignment, such that the first through 4th elements represent PT/Exercise, MSBR, Acupressure, and Duloxetine treatment status. The vector  $X_{2i}$  contains the baseline covariates for subject  $i$  at time 2 (sex, age, BMI, race, and education) and  $Y_{2i}$ . For  $t \in \{2, 3\}$ , the matrix  $Z_{ti}$  will hold subject  $i$ 's time  $t$  measurements of the hypothesized treatment modifiers.  $Z_{ti}$  will have 7 total columns that correspond to the hypothesized treatment modifiers, and the columns will be specified such that the element-wise product  $A_{ti} \cdot Z_{ti}$  represents the 8 hypothesized treatment-phenotype interactions.

We jointly model data at T3 and T4 to gain efficiency in estimating the main effects of treatment, the main effects of the potential moderators, and the interaction effects between treatment and the potential moderators in stage 1. The main effects of treatment and covariates are allowed to differ between stages, but we assume these effects are additive. In contrast, treatment-by-phenotype interaction effects are assumed to be the same across both stages. We propose the following model:

$$\begin{aligned} E[Y_{3i}] &= X_{2i}^T \beta_2 + A_{2i}^T \phi_2 + Z_{2i}^T \varphi_2 + (A_{2i} \circ Z_{2i})^T \psi_2 \\ E[Y_{4i}] &= X_{2i}^T \beta_2 + A_{3i}^T \phi_2 + Z_{3i}^T \varphi_2 + R_i^T [A_{3i}^T \phi_{3R} + Z_{3i}^T \varphi_{3R}] \\ &\quad + (1 - R_i)^T [A_{3i}^T \phi_{3NR} + Z_{3i}^T \varphi_{3NR}] + (A_{3i} \circ Z_{3i})^T \psi_2 \end{aligned}$$

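### Change in PEG from T2 to T3 is a named secondary endpoint, but both assessment schedules leave PEG unmarked at T2 and T3

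*SAP*

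**What the plan says.** **Endpoint.** The Protocol synopsis lists as a secondary endpoint "Change in the Pain, Enjoyment and General Activity (PEG) Scale between T2 and T3 study visits". SAP 4.3 agrees: the "secondary endpoints consist of the change in the Pain Intensity (PEG) and the Patient Global Impression of Change (PGIC"), over the same interval.

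**Analysis.** SAP 9.1 states that "The analysis will be repeated for the secondary pain outcomes", PEG being one of them. In SAP 9.1.1 the covariate vector holds the baseline variables "at time 2 (sex, age, BMI, race, and education) and" the T2 value of the outcome. The outcomes modelled are the T3 and T4 values. Objective 2 (SAP 9.2) is also repeated for PEG and adjusts for the baseline outcome at T2. SAP 6.1 names PEG change in its power statement.

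**Schedule.** In SAP Table 1 the row "Pain Intensity (PEG") is marked at T1, Deep Visit 1, Deep Visit 2, T4, T5 and the week-12 expanded mini-assessment. T2 and T3 are blank. The PEG row in Protocol 1.3 has the same pattern.

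**Which text governs timing.** Protocol 12 says in general terms that questionnaires are completed at T1 to T5, but it sends the reader to Section 1.3 for the time points of each measure. Protocol 6.1 also refers to Section 1.3.

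**The concern.** The endpoint is a difference between two visits, and the schedule does not call for the instrument at either of them. Only the deep subset attends the deep visits where PEG is marked. Protocol 10 places those visits off the T2 and T3 visits themselves: "There will be two visits that take place after T2-before Treatment 1 and after T3-before Treatment 2".

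If the surveys were built from the schedule as printed, a light-only participant would have PEG at T1 (week 1), week 12, T4 and T5, and at neither end of the T2–T3 interval. The repeated Objective 1 model would have no complete row for that participant: the T3 row lacks both outcome and covariate, and the T4 row lacks the T2 covariate. A named secondary endpoint would then rest on the deep subset or on imputing both ends for most of the trial.

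**Working it through.** **1. SAP Table 1, cell by cell.** The column header survives: T2 is column 4, Deep Visit 1 column 5, T3 column 8, Deep Visit 2 column 9. The PEG row has all 20 cells.

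| SAP row | T1 | T2 | Deep 1 | T3 | Deep 2 | T4 | T5 | Week 12 |
|---|---|---|---|---|---|---|---|---|
| PEG | x | – | x | – | x | x | x | x |
| Current opioid use | x | x | x | x | x | x | x | x |
| PROMIS Pain Interference | x | x | x | x | x | x | x | x |
| PROMIS Social Role | x | x | – | x | – | x | x | x |
| PHQ-2 | x | – | x | – | x | – | – | x |

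PEG and the opioid-use row directly above it differ in exactly two cells, T2 and T3. PROMIS Pain Interference, the primary measure, is marked at both.

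**2. Protocol Table 1.** The header is missing from the text available, so only cell positions can be compared. PEG is marked in 1, 4, 7, 9, 12, 14 and opioid use in 1, 3, 4, 6, 7, 9, 12, 14, so they differ at positions 3 and 6 only. To identify these positions, take "PROMIS Social Role Activity". In the SAP that row is marked at T2 and T3 and at neither deep visit. In the Protocol it is marked at 3 and 6 and blank at 4 and 7. Positions 3 and 6 are therefore T2 and T3.

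**3. Could the visit window rescue it?** SAP 5.6 allows ±2 weeks, which gives weeks 4–8 for T2 (week 6) and 13–17 for T3 (week 15). For light-only participants the nearest PEG readings are week 1 (6 − 1 = 5 weeks early) and week 12 (15 − 12 = 3 weeks early), both outside. Deep-visit readings, scheduled in weeks 6 and 15, could fall inside.

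**4. How many, if the schedule was followed as printed.**
- PEG around both ends of Treatment 1: at most 160/408 = 39.2%, or 160/4 = 40 per arm.
- Without it: 408 − 160 = 248, and 248/408 = 60.8%.
- The SAP 7.4 level for multiple imputation: 0.15 × 408 ≈ 61 participants.

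**5. Power.** For a two-sided 5% test of a correlation, Fisher z gives power = Φ(atanh(r)·√(n − 3) − 1.96).
- The plan's figure, r = 0.28, n = 102: 0.2877 × 9.950 − 1.96 = 0.902, power 81.7% (simulation 81.9%, noncentral t 83.1%). SAP 6.1 says at least 80%, so it reproduces.
- The plan's deep-subset figure, r = 0.42, n = 40: 0.4477 × 6.083 − 1.96 = 0.763, power 77.7% (simulation 78.7%, noncentral t 81.4%). SAP 6.1 says 80%, so it reproduces to within about 2 points.
- r = 0.28 with n = 40: 0.2877 × 6.083 − 1.96 = −0.210, power 41.7% (simulation 42.4%, noncentral t 43.6%).

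These are single-arm correlation figures, as in SAP 6.1, and not the power of the GEE interaction test.

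**The case against.** The strongest reply is that intent is clear. Every mention of PEG outside the tables either defines the T2–T3 endpoint or plans an analysis that needs it, and an endpoint definition is itself a reason to collect the data. On that reading this is an editorial slip and the missing-data figures are hypothetical. That is probably right about the cause, and the figures are conditional. But the Protocol points to the schedule for timing, and nothing in either document corrects it. Nor does the table itself show a blank to be an error: the row for "Questionnaire-2 (PHQ-2") on the same page is also empty at T2 and T3 and marked at both deep visits. PHQ-2 is not a T2–T3 endpoint, so its blanks conflict with nothing. They show only that this pattern can occur in the table without contradiction.

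A second reply is that the tables are unreliable as read. The Protocol header is lost, and in the SAP's deep-phenotyping block some deep-only tests, such as fMRI, fall under T2 and T3, one column out. The Protocol evidence is indeed inferred and weaker than the SAP's. Column drift is still a poor explanation for the PEG row. Its T1, T4, T5 and week-12 marks sit in the right columns, it matches the opioid-use row everywhere else, and the same two cells are empty in both documents.

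A third reply is that SAP 7.4 prescribes multiple imputation above 15% in the primary analyses, and PEG is secondary. That is a fair reading of the sentence. However, SAP 8.3 counts missing data among protocol deviations and applies imputation above 15% to versions of the primary and secondary analyses, and the missing-data text in Protocol 18.1.5 has no such limit. Imputation could draw on PEG at other visits and PROMIS Pain Interference at T2 and T3, but both ends of the endpoint would be imputed for most participants.

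**Conclusion.** The concern holds. The endpoint definition and the schedule contradict each other, firmly in the SAP and by inference from neighbouring rows in the Protocol. Whether data are affected cannot be told from the documents.

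- If PEG is in the T2 and T3 surveys, the effect on the data is nil.
- If the schedule was followed as printed, PEG is marked at T2 or T3 for none of 408. At most 160 (39%) have deep-visit readings around Treatment 1, and 248 (61%) lack them. Without imputation, the 102-per-arm power statement would not apply to PEG change, and power at r = 0.28 would be about 42% instead of about 82%.

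This assumes the SAP's total of 408, all 160 deep participants randomized and spread evenly over four arms, and no other loss. The primary endpoint is not touched. The point should be fixed because a named secondary endpoint depends on it and the correction costs almost nothing.

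**What to change.** Mark PEG at T2 and T3 for all participants in SAP Table 1 and Protocol Table 1, after checking both against the source tables. Confirm that the T2 and T3 online surveys contain PEG.

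If it was not collected there, state in the SAP that the PEG change analysis is limited to the deep subset, that deep-visit readings stand in for T2 and T3, and that the 40-per-arm figure already in SAP 6.1 (r = 0.42) applies to it.

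The cost is two cells in each table and a check of two existing surveys or, in the second case, one or two sentences in the SAP.

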## 5 Study Methods

### 5.1 General Study Design and Plan

We will conduct a 36-week pragmatic trial in a cohort of cLBP patients (see Figure 1 and Figure 2). The proposed SMART will consist of a 4-week run-in period using an online cognitive-behavioral self-management intervention (PainGuide), followed by two 8-week treatment periods. All participants will be followed for a total of approximately nine months.

At baseline (T1), approximately 500 patients will undergo a comprehensive baseline phenotyping assessment. After receiving PainGuide (access to an online self-management program) for 4 weeks, each participant will complete a light phenotyping assessment (T2) and a subset of these patients (n=160) will complete an additional deep phenotyping assessment. Those who still have significant pain interference ( $\geq 2$  from Patient Global Impression Scale, PGIC) will be randomized to one of the four 8-week long interventions (i.e., Mindfulness-Based Stress Reduction (MBSR), Physical Therapy (PT)/Exercise, Acupressure self-management [eHealth app], or Duloxetine). Participants with a PGIC=1 will not be randomized and continue with long-term follow-up. The PainGuide run-in is designed to provide the lightest “touch” intervention and to help control for regression to the mean. We will use block randomization with random block size of 4 and 8. Approximately 102 patients will be assigned to each treatment group including Physical Therapy/Exercise, MBSR, Acupressure, and Duloxetine treatment groups. For addition details, please see Section 6.3.

Following the first 8-week treatment period, patients will be reassessed (T3) using light only or light plus deep assessments (for the subset of 160) and those still having significant pain interference ( $\geq 2$  from Patient Global Impression Scale [PGIC]) will be re-randomized to receive one of the three treatments they did not receive in the first treatment period. Participants with a PGIC=1 will not be randomized and continue with long-term follow-up. After the second intervention and three months later, all undergo the light phenotyping follow-up assessment protocol (T4). Lastly, a final assessment will take place at 3 months after the scheduled end of the second 8-week treatment period (T5). There will also be a series of interim assessments that take place at 2-week intervals in between the regular assessments (T1-T5).

The study aims to identify which interventions are most efficacious for different patient phenotypes. The primary analysis will explore how treatment response depends on patient phenotype. Secondary analyses will compare dynamic treatment regimens by patient phenotype. The SMART study does not include a control group because the efficacy of the four treatments has already been shown for the population of cLBP patients.

[figure not shown]
Study team members will not be blinded to patient treatment assignment.

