We will fit the model for all repeated measures ( $Y_{3i}, Y_{4i}$ ) using generalized estimating equations (GEE) with a working independence covariance matrix through the R package *gee*. We will use robust standard errors for variance estimation to account for the use of repeated measures. Prior to conducting inference, we will assess the functional forms of the predictors and the validity of the assumptions required for joint stage modeling, especially the assumption of constant interaction effects across treatment stages. If the assumptions for joint modeling are violated, we will conduct the primary analysis with stage 1 data only. For inference, we additionally assume  $Y_{3i}, Y_{4i}$  follow a multivariate normal distribution.

The clinical objective of Aim 1 is to show that patient responsiveness to treatment depends on their

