### 11 Other Analyses

Exploratory, we will analyze the 12 embedded dynamic treatment regimens within the SMART design using the joint model described in section 10.1.1. Additionally, we will consider further tailoring of the embedded dynamic treatment regimens using augmented outcome-weighted learning.

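### The model named for comparing the 12 embedded regimens conditions on T3 response and T3 phenotype, leaves out the first treatment and has no averaging or weighting step, so as written it does not deliver regimen means

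*SAP*

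**What the plan says.** SAP 5.1 promises the comparison: "Secondary analyses will compare dynamic treatment regimens by patient phenotype". SAP 11 gives the method: "Exploratory, we will analyze the 12 embedded dynamic treatment regimens within the SMART design using the joint model described in section 10.1.1". Section 10.1.1 is the definition of serious adverse events; the joint model is in 9.1.1. Section 5.1 calls the analysis secondary and section 11 calls it exploratory. Section 11 also names augmented outcome-weighted learning, but only for further tailoring of the regimens.

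In 9.1.1, R is introduced to "denote response status at T3", and Z holds each participant's "measurements of the hypothesized treatment modifiers" at T2 or T3. The T4 mean has terms in X2, A3, Z3, R by (A3, Z3), (1−R) by (A3, Z3), and A3 by Z3. A2 does not appear. The fit uses "generalized estimating equations (GEE) with a working independence covariance matrix" and robust standard errors; no weights are named.

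At T3, participants with PGIC≥2 "will be re-randomized to receive one of the three treatments they did not receive in the first treatment period"; those with PGIC=1 are not re-randomised. Protocol 8.1 adds that allocation probabilities allow for participants who are eligible for only three treatments.

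**The concern.** A regimen here means: start treatment a; if PGIC≥2 at T3, switch to b. Its mean T4 outcome averages over who responds to a and over the phenotype that a leaves behind at T3. The T4 equation holds both fixed, and the SAP has no model for either given the first treatment.

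Section 9.1.1 justifies modelling T3 and T4 together as a gain in efficiency for stage 1 effects. Section 11 reuses that model for a different quantity without defining a regimen mean or contrast. SAP 9.2 does adjust T4 for the first treatment, by response status, so carry-over is recognised there but not here.

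A first treatment that works by producing more responders, or by shifting the moderators, would receive no credit in contrasts read from the T4 coefficients. The comparison that uses the SMART structure could then rank regimens wrongly. A comparison by phenotype is also useful only at the phenotype known when a regimen is chosen (T2), whereas the T4 equation's moderator terms are in Z3.

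**Working it through.** **Count.** SAP 7.5 gives 16 pathways and 12 regimens. Four first treatments × 3 switches = 12 regimens; 12 non-responder pathways + 4 responder pathways = 16. Both figures reproduce.

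**What is needed.** For regimen (a, b):

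μ(a,b) = P(R=1|a)·E[Y4|a, R=1] + P(R=0|a)·E[Y4|a, R=0, b],

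with each expectation taken over the Z3 distribution that a produces.

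**What the T4 equation gives.** Set R=0, X2=x, Z3=z and second treatment b. Every remaining term depends on x, z and b, and none on a. The 12 non-responder pathways therefore collapse to 4 values, one per second treatment. For (a, b) against (a′, b) the contrast is exactly 0. This follows from the equation and needs no assumption about the data.

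**Size of the part acting through response.** Take two regimens with the same second treatment, first-treatment response rates q and q′, and responders g points lower at T4. The true difference is (q′−q)·g. The documents give neither q nor g, so these are assumptions:
- q=5%, q′=15%, g=5: 0.10 × 5 = 0.5 points
- q=10%, q′=30%, g=10: 0.20 × 10 = 2.0 points

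The conditional contrast is 0 in both.

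**Weights.** When all four treatments are open, a responder's path has probability 1/4 and a re-randomised non-responder's has 1/4 × 1/3 = 1/12. The inverse-probability weights are 4 and 12.

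**Illustrative simulation.** Assumed: response of 5, 10, 20 and 30% by first arm; responders 7 points lower at T4; first treatment shifts Z3; responders keep their first treatment as A3 (9.1.1 does not say how A3 is coded for them). Carry-over, where present, lowers T4 by 0, 1, 2 or 3 points by first arm. Four pairs with a common second treatment were compared:

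| Estimate of the T4 difference | No direct carry-over | With direct carry-over |
|---|---|---|
| Truth | −1.3 to −2.8 | −3.3 to −5.8 |
| 9.1.1 model at R=0, fixed Z3 | 0 | 0 |
| Weighted by 4 and 12 | within 0.1 of truth | within 0.1 of truth |
| 9.1.1 model averaged over R and Z3 within first arm | within 0.1 of truth | −1.6 to −3.5 |

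**Precision for scale.** With weights, the variance of a regimen mean is about (SD²/n)·{q + 3(1−q)} = (SD²/n)(3−2q). Take n=102 per arm, SD=10 (the PROMIS population value in SAP 8.2, assumed to hold at T4), and q of 10% and 30%. The variance of the difference is (100/102)(2.8+2.4) = 5.10, so the standard error is about 2.3 points.

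**The case against.** A regression of T4 on history is the usual second-stage input to g-computation or Q-learning, which need no weights. On this view SAP 11 only leaves an averaging step unstated. This stands in part: missing weights alone are not fatal, and averaging the 9.1.1 model within each first arm worked in the simulation without carry-over. But no such step is planned, and with A2 absent it fell well short once carry-over was present. A reader might infer that this model could never yield a regimen mean. The documents do not support that, because standardisation with A2 in the model would do so.

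Other parts of the objection also stand:
- The exact zero comes from A2 being absent. Adding A2 by R, as in 9.2, removes the zero, but the contrast would still be conditional on R and Z3.
- Not every contrast is compromised. Of the 66 pairs of regimens (12×11/2), 12 share a first treatment (4×3). Conditioning on R=0 and Z3 does no harm there, because re-randomisation follows both. Such a contrast speaks for non-responders only.
- A reader might infer that unweighted pooling of regimen-consistent participants is planned. It would over-represent responders: 0.10/(0.10+0.90/3) = 25% and 0.30/(0.30+0.70/3) = 56%, which turns the 2.0-point example into 3.1. No section proposes this.
- Nor does the SAP state that contrasts will be read at fixed R and Z3, or phenotype at T3. It states no regimen contrast at all.
- A standard error near 2.3 points means that rankings will be uncertain under any estimator, and SAP 7.5 concedes low power for interactions.

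**Conclusion.** The concern holds as a defect in the method named for the regimen comparison, and it should be corrected. The 9.1.1 model as written yields conditional second-stage effects, and nothing in the SAP turns them into regimen means. The zero contrast between regimens with the same second and different first treatments, at R=0 and fixed Z3, is structural. The amount missed is not: 0.5 to 2.0 points through response in the two examples, and more if the first treatment also shifts Z3 or carries over. These sizes rest on assumed response rates and responder gaps, and low PGIC=1 rates would shrink the part acting through response.

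A reader might extend this to the trial's main result. The documents do not support that: the primary and secondary endpoints are T2–T3 changes, and SAP 11 labels the regimen analysis exploratory. That label still conflicts with SAP 5.1 and should be reconciled.

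**What to change.** In SAP 11, define the regimen mean at T4, correct the cross-reference to 9.1.1, settle with 5.1 whether the analysis is secondary or exploratory, and name one estimator:

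- **(a) Weighted-and-replicated GEE** with regimen indicators, X2, and T2 phenotype with its regimen interaction, omitting R and Z3. Weight T3 responders (PGIC=1) by 1/P(A2) and re-randomised non-responders by 1/{P(A2)·P(A3)}. Use each participant's actual allocation probabilities; the values are 4 and 12 only when all four treatments are open. Replicate responders only across regimens feasible for them, and cluster robust errors on participant.
- **(b) Standardisation** of a T4 model that includes A2 by R, as in 9.2, averaged over R and Z3 within each first arm.

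In either case:
- treat non-responders who leave before T3 randomisation as missing data, not as responders;
- limit each regimen comparison to participants eligible for the treatments involved;
- read phenotype at T2.

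The cost is SAP wording, routine programming and a record of each participant's allocation probabilities. Option (a) loses some precision.
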